8. Randomization: After medical clearance to participate, subjects will be randomized to either of two parallel groups, treatment with Muscle Armor or placebo. The double-blind randomization will be performed by a research pharmacist. Assignments will be unknown to investigators and subjects. The pharmacist will review all study material prior to approval, and can break the blind if needed for safety purposes, but is otherwise uninvolved in the study. The pharmacist will dispense the products in sealed and blinded packaging. The study will appoint a study monitor (specific un-blinded member of the study team) to review and be involved in pharmacy and subject compliance. This person will not be involved in subject assessments or specimen analysis.

9. Supplementation: Muscle Armor was chosen from a scientific standpoint because of the ability of its ingredients to modulate muscle health and immune function. Muscle Armor is a good choice for practical purposes because its ingredients are safe to consume [46;47] and it is available to individuals by retail.

- a. Subjects in the supplement group will consume orange-flavored Muscle Armor according to the manufacturer's directions: one serving (approximately 30g, i.e. one scoop provided with the product by its manufacturer), twice daily (optimally morning and evening), mixed with 12 ounces (oz) of water. Subjects in the placebo group will similarly consume one serving (approximately 13g, one scoop provided to pharmacy by the study) of orange-flavored Kool-Aid mixed with 12 ounces of water twice daily.
- b. Quality control weighing of single doses of supplement and placebo indicates that exact dose will vary based on whether a level, sub-level, or heaping scoop is used and this is acceptable. Dose range for the supplement appears to be 30-35 grams and dose range for the placebo appears to be 11-15 grams. This is less than the actual single serving size listed on the instructions for Kool-Aid but is deemed acceptable due the sugar content of the recommended serving size since diabetics will likely be enrolled and older adults may dislike the taste due to it being too sweet.

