- c. Supplementation will typically begin the day of the second muscle biopsy (typically Visit 5) and continue for the remainder of the participant's study involvement (optimally approximately 42 weeks). The total dosing time will likely be longer than the optimal time because scheduling of the exercise training and other appointments must be performed based on VA holidays, patient and physician availability, etc. And specific starting date or intermittent dosing lengths of time can be altered without protocol deviation in order to maintain proper spacing of the more time dependent clinical procedures, e.g. blood draw, biopsy, and vaccination.
- d. Compliance will be monitored using subject self-report and both the number of doses consumed and weight of product consumed. Each canister will contain 14 doses (7 day supply) though

this number is approximate due to the inexact measurement of one scoop. Canisters will contain 421 grams of supplement or 188 grams of placebo. Subjects will return empty containers. Containers will only be weighed if unused supplement or placebo is returned. Self-report will be based on completion and return of the dosing calendar. This information will be collected and reviewed by a study monitor, i.e. member of the study team who is not blinded. The monitor is planned to review dosing and consumption for compliance with the subject approximately every four weeks by phone or in person or more often as needed. Subject diet data will not be collected but to be involved subjects must agree to maintain their normal diet during participation.

- e. Subjects will be given a gym bag to transport their canisters of supplement/placebo and consumption calendar between home and study visits. They will also be given two drink mixer bottles of the type commonly used to mix powder shakes. These products contain the GRECC name and phone number of the study coordinator. Subjects will be allowed to keep the bag and bottles upon completion of the study. The approximate value of the products per subject is ~\$28. These gifts are justified due to making it easier for the subject to transport materials to and from study visits which should increase subject compliance with dosing and monitoring requirements.

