- f. 06/12/2017 Modification. The study has learned that Abbott Nutrition is no longer manufacturing Muscle Armor and will only sell a similar product, Juven, in the future. The study will switch to using Juven with approval of this modification though remaining stores of Muscle Armor will be used until expiration date. The study had originally planned to use Juven but did not use Juven after learning that it is only available in single serve packets which would make the blinding process laborious. Use of Juven will require the study team member who packs the placebo in the pharmacy to pack the supplement Juven in similar fashion, i.e. 14 doses (packets) will be emptied into the usual blinded supplement canisters. Other pertinent details of the switch include the following:
 - i. Juven and Muscle Armor are essentially the same product but were being marketed by the company under two different names. They taste, smell, and look identical. Thus, the blind will not be in jeopardy due to the switch.
 - ii. The key ingredients of interest (Arginine, Glutamine, Methylbutyrate) are present in the same amounts in Juven and Muscle Armor. Juven lacks the 3g Taurine that is in Muscle Armor and Juven contains phenylalanine, and FD&C Yellow #6 instead of Red #40, and aspartame instead of sucralose.
 - iii. The product identity and ingredients were not mentioned in the consent form or other information given to subjects.
 - iv. Since Taurine is missing in Juven, the dose size is slightly smaller than Muscle Armor (24g versus 30 g). However, Juven was measured in the same scoop size used for Muscle Armor and the difference was negligible.
 - v. Switching to a slightly different product during the study is not optimal but is necessary. The switch is not expected to affect the results. However, the study will track when the switch was made for each subject to determine during statistical analysis if a bias was introduced.
- g. **Benefit:** The subjects may or may not have improved muscle health and immune function due to the supplement. The supplement may improve the response to the vaccine. However, it is unknown whether this improvement will convey increased protection from disease.

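### The 421 g canister weight was not carried through the switch to Juven, and the 24 g dose conflicts by weight with a negligible scoop difference

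*Combined protocol and SAP*

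**What the plan says.** All of this is in the protocol under Human Subject Aspects of the Study, item 9 (Supplementation).

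- **9.a and 9.b, Muscle Armor dose.** Subjects take "one serving (approximately 30g, i.e. one scoop provided with the product by its manufacturer), twice daily". On quality-control weighing, "Dose range for the supplement appears to be 30-35 grams"; the spread between level and heaping scoops is accepted.
- **9.d, canister and compliance.** "Canisters will contain 421 grams of supplement or 188 grams of placebo". "Each canister will contain 14 doses (7 day supply) though" "this number is approximate due to the inexact measurement of one scoop". Compliance is followed by self-report, number of doses and weight of product consumed. A container is weighed only if it comes back with product in it. An unblinded monitor does the review.
- **9.f, change to Juven (06/12/2017).** Remaining Muscle Armor is used until it expires. For Juven, "14 doses (packets) will be emptied into the usual blinded supplement canisters".
- **9.f.iv, dose size.** Because taurine is absent, "the dose size is slightly smaller than Muscle Armor (24g versus 30 g"). The next sentence says that "Juven was measured in the same scoop size used for Muscle Armor and the difference was negligible".
- **Table 2.** Arginine (7 g), glutamine (7 g) and calcium HMB (1.5 g) per serving are the same in both products. Carbohydrate is 10 g in Muscle Armor and 8 g in Juven. The footnote gives taurine as the only difference.

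The modification gives no canister weight for Juven and no weight for a scoop of Juven.

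**The concern.** Two things do not fit.

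First, 9.d still gives one supplement canister weight, without naming a product, and names weight as a compliance measure. After the switch the canister holds a product with a lighter serving, so the stated starting weight is wrong for it. Read literally, 9.d biases weight-based compliance upward in one arm.

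Second, 9.f.iv reports a dose one fifth lighter and then dismisses the difference in the scoop. Subjects dose by scoop, not by packet, so the weight of Juven in a scoop determines the dose taken and how long a canister lasts. The text leaves that weight unknown. Item 9.f.v plans to examine whether the switch introduced bias, and that analysis needs the dose actually delivered before and after the switch.

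**Working it through.** **Inputs.** 14 doses per canister, two per day (9.a, 9.d); supplement canister 421 g (9.d); Muscle Armor serving about 30 g (9.a), scoop 30-35 g (9.b); 14 Juven packets per canister (9.f) at 24 g (9.f.iv); contents per serving from Table 2.

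**1. The plan's own figure.** Canister weight = doses x grams per dose.

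- Muscle Armor: 14 x 30 = 420 g, against 421 g stated (421/14 = 30.07 g per dose). The figure is reproduced.

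**2. The same formula for Juven.**

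- 14 x 24 = 336 g.
- Shortfall: 421 - 336 = 85 g; 85/421 = 20.2%.
- 421 g would need 421/24 = 17.5 packets.

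**3. Effect on weight-based compliance.** Consumption = starting weight - returned weight. If r grams come back, true consumption is 336 - r and the figure using 421 g is 421 - r. The error is 85 g whatever r is.

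- In doses: 85/24 = 3.5 doses of 24 g, or 85/30 = 2.8 doses of 30 g.
- An unopened Juven canister would read as 85 g consumed.
- A half-used one (168 g returned) would read as 421 - 168 = 253 g, or 10.5 doses of 24 g, when 168 g (7 doses) had been used.
- An empty container is not weighed, so it is not affected. The placebo weight (188 g) does not change with the switch.

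**4. The scoop statement.** By weight, (30 - 24)/30 = 20%, which is not a negligible difference. What follows depends on the weight s of one Juven scoop. Doses = 336/s; days = doses/2; content relative to a packet = s/24.

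| Juven scoop, s | Doses | Days | Content relative to packet | Arginine or glutamine | HMB |
|---|---|---|---|---|---|
| 24 g | 14.0 | 7.0 | 1.00 | 7.0 g | 1.50 g |
| 30 g | 11.2 | 5.6 | 1.25 | 8.75 g | 1.88 g |
| 35 g | 9.6 | 4.8 | 1.46 | 10.2 g | 2.19 g |

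Part of the last row is not due to the switch. With Muscle Armor, a 35 g scoop already gives 35/30 = 1.17 times the serving and cuts 421 g to 12.0 doses (6.0 days), within the variation that 9.b and 9.d accept. Since 1.46 = 1.25 x 1.17, the part that the switch could add is the factor 1.25.

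**5. The stated reason for the lighter dose.** Taurine accounts for 3 g of the 6 g difference. Table 2 shows a further 10 - 8 = 2 g of carbohydrate, which contradicts its own footnote. Item 9.f.ii also lists differences in phenylalanine, colouring and sweetener.

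**The case against.** The strongest reply is that nothing was miscalculated. The protocol nowhere says that 14 Juven packets weigh 421 g. That figure is right for Muscle Armor and still applies to the remaining stock. The monitor is unblinded and the study records when each subject changes product, so the right starting weight could be used in practice. Weight is also only one of three compliance measures. All of this stands, and it is why the point is minor. It does not remove the gap: 9.d gives one weight for the supplement, and no other is available to whoever applies it.

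Three stronger readings are tempting, and the documents do not support them.

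- **That Juven subjects ran out early on larger doses.** A scoop measures volume. The sentence in 9.f.iv can mean that a 24 g packet fills about the same scoop, which agrees with 9.f treating a dose as a packet. Then 14 scoops last 7 days at the Table 2 content. The sentence follows a comparison in grams and is set against it, so a weight reading is also natural. No Juven scoop weight is given to decide between them.
- **That a fully used Juven canister would be misread.** Under 9.d it would not be weighed.
- **That the claim of equal key ingredients is unsupported.** Item 9.f.ii makes a statement about composition, and Table 2 supports it per serving. What is open is whether one scoop is one serving.

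**Conclusion.** Wrong as written, and minor. Two parts are certain on the stated figures. The 421 g weight does not apply to a Juven canister, which holds 336 g at the 24 g dose size. And a 24 g against 30 g dose cannot be reconciled, by weight, with a negligible scoop difference.

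The compliance error is 85 g per returned Juven canister that still contains product, always towards overstated consumption and only in the supplement arm. This assumes that the monitor uses 421 g as the starting weight, as 9.d reads, and that packets weigh 24 g.

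The consequences for dosing are conditional. If a Juven scoop weighs 30-35 g, a canister gives 9.6-11.2 scoops (4.8-5.6 days) at 1.25-1.46 times packet content, part of which is scoop variation already accepted. If it weighs about 24 g, there is neither early depletion nor excess content. The documents do not settle which holds, and no view is taken here on which dose is right.

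**What to change.** 1. Weigh a scoop of Juven (level to heaping, as was done for Muscle Armor) and a filled Juven canister, and record both in item 9.
2. State in 9.f.iv whether the scoop comparison was by weight or by volume.
3. In 9.d, give a canister weight for each product and compute weight-based compliance from the one dispensed. Both are needed, because Muscle Armor stock is used until it expires. Where a returned Juven canister has already been judged against 421 g, recompute it; the switch record in 9.f.v identifies the subjects.
4. Reconcile 9.a, 9.b, 9.d, 9.f and Table 2, including the footnote that only taurine differs. The study physicians and pharmacist decide the dosing instruction.
5. Carry the measured scoop weight into the planned check for bias from the switch.

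The cost is a short session of weighing, a wording change, and recalculation for any affected canisters. Design, sample size and main analyses are unchanged.

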- (10) Taking Fish Oil, Gingko, Garlic, Saw Palmetto, Turmeric, or Vitamin E and unable or unwilling to discontinue use for 10 days prior to the muscle biopsy procedure. Multivitamin containing vitamin E is acceptable and does not need to be halted.
- (11) Significant history of fainting
- (12) Significant problems with chronic pain
- (13) Uncontrolled asthma or allergies
- (14) Taking lactulose, nitrates plus hypertension medications or Viagra
- (15) Liver cirrhosis or other severe liver disease
- (16) History of peripheral artery disease
- (17) Steroid or androgen use in past 3 months that physician feels may confound study
- (18) Other physician judgment

e. **Other Exclusion Criteria: information collected during the physical exam by the study physician or qualified designee.** Blood will be drawn (less than or equal to 60ml or 2 ounces) for lab analyses by the hospital clinical lab at study entry, after completion of the exercise training program, and upon completion of the study for tests related to eligibility, safety, and research data.

- (1) Blood Pressure greater than 160/100 or <100 systolic.
- (2) HbA1C>10
- (3) CBC or PT/PTT/INR results that the study physician determines indicate a risk for excessive bleeding.
- (4) Clinical labs performed for safety monitoring including AST, ALT, creatinine, and BUN
- (5) Other tests that performed to measure immune function include HbA1C, CBC, CRP, ESR, cholesterol HDL and LDL, and blood differential.

f. **Exclusion Criteria Based on Other Physician Judgments:** older veteran subjects often possess numerous comorbidities that result in a complex and unique set of health issues. Thus, in addition to the specific exclusion criteria named above, the physician must also use a considerable amount of judgment in determining whether a recruit should be excluded even though the recruit meets the named inclusion criteria and does not meet the named exclusion

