criteria. The physician also makes such judgments to determine if a subject should be withdrawn once participation has begun. The physician may obtain any additional unforeseen medical information that may be needed at enrollment or during participation. As explained in the consent and HIPAA documents, this information may be collected through CPRS, additional examinations or tests, or by consultation with the subject's healthcare providers from inside or outside the VA. As appropriate, the physician will document and use this information to judge whether the subject can safely participate, should be excluded or withdrawn, or should be referred for treatment.

6. Scheduling: A scheduling calendar will be used by the study staff and study visit scheduling cards will be given to the subjects to help ensure compliance with study visits and procedures.

- a. A subject scheduling calendar will be maintained in the form of an Excel spreadsheet. The calendar is needed in order for the study team to coordinate study procedures and data collection particularly when multiple subjects are scheduled for any one day. Thus, the calendar will improve study efficiency, subject safety, and care. The calendar will contain dates, subject ID #, and procedures for each visit. It will be stored in the PI's secure folder containing electronic logs.
- b. The study will also give patients visit cards that will include subject name, visit date and time for up to three visits, procedures, and estimated time required. The calendar and cards will help keep the study team and subjects on track with the study requirements for each visit.
- c. The scheduling cards will typically be hand given to subjects at an appointment when their next appointment time and date is already known. However, scheduling cards may also be mailed, as needed, for instances when an appointment must be scheduled over the phone and the subject desires a written reminder in addition to the reminder telephone calls that are already commonly used. Obviously a card would not be mailed, for example, if a subject is contacted by phone and states that a card is not needed or if the appointment is scheduled for so soon as to not allow time for mail to be received.

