h. **Risk:** There is little evidence from controlled studies of risk associated with the ingredients of the supplement. However, adverse events have occurred in which the relation to underlying disease or the supplement was not discerned. Thus, this study will take a conservative approach and consider that the ingredients may exacerbate the following conditions: allergies or asthma, herpes, and low blood pressure. The supplement may cause side effects such as abdominal pain, bloating, diarrhea, gout, blood abnormalities, sensitivity similar to monosodium glutamate (MSG; headache, flushing, tingling, weakness). Caution should be used when taking the supplement and lactulose. The supplement should not be taken by individuals undergoing chemotherapy, or those having a recent heart attack, liver disease, seizures, mania or bipolar disorder and taking lithium.

i.

Table 2. *Comparison of nutrient information between Muscle Armor supplement and Kool-Aid placebo control for one serving mixed with 12 oz water. Juven ingredients listed in parentheses.

MUSCLE ARMOR	PER SERVING	KOOL-AID	PER SERVING		
AMINO ACIDS			AMINO ACIDS		
L-ARGININE	7 (7)	g	L-ARGININE	0	G
L-GLUTAMINE	7 (7)	g	L-GLUTAMINE	0	G
TAURINE	3 (0)	g	TAURINE	0	g
CARBOHYDRATE	10 (8)	g	CARBOHYDRATE	16	g
SUGARS	5 (2)	g	SUGARS	16	g
MINERALS			MINERALS		
CALCIUM	200 (200)	mg	CALCIUM	0	mg
Calcium β -hydroxy- β -methylbutyrate	1.5 (1.5)	g	Calcium β -hydroxy- β -methylbutyrate	0	g
VITAMIN C	0 (0)	mg	VITAMIN C	9	mg
ENERGY	110 (80)	kcal	ENERGY	60	kcal

*Juven supplement has the same composition as Muscle Armor except it lacks Taurine.

j. **Minimization of risks:** The risks of participation will be minimized by cautious consideration of the potential adverse effects of Muscle Armor by the study physician during enrollment and monitoring. Individuals who should not take the supplement will be excluded. Subjects will be informed of the potential side-effects and advised to report any symptoms. Symptoms related to the supplement and other study procedures will be monitored for, as applicable, at each study appointment and by attempted telephone contacts weekly. Safety monitoring will also include blood draws for assessment of liver and kidney function at baseline, after completion of the training program and at the end of the study.

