- c. **Unaccustomed Exercise Sessions (2x):** Prior to exercise training, the study will measure the response to single bouts of the training exercises before and after two weeks of nutritional supplementation. The response to exercise will be measured using both muscle and blood. The pre-exercise time points will be prior to exercise, possibly same day or a different day based on scheduling and/or the judgment of the study physician. The post-exercise time points for collection are 72 hrs for muscle and 1 hr for blood. Our studies have previously shown that 72 hrs is a better than 24 hours for measuring the immune variables of interest in muscle [52].

The 1 hr time point for blood collection is based on other studies that have determined the effects of exercise on systemic measures of immune function [11;53].

- d. **Exercise Training Sessions (36x):** The training program plans to have subjects perform supervised exercise at the NLR VA for approximately an hour optimally 3 times per week on non-consecutive days. The program consists of 36 exercise sessions that will optimally take 12-weeks though the total time will likely be longer due to rescheduling based on the needs of the subject or the study team.
- e. The exercise load will be based on how much the subject is capable of lifting one time. After strength testing, subjects will perform exercises at loads ranging from 60% to 80% (e.g. sets at 60, 70, 75, and 80% of capability) of their measured capability to the best of their ability. Strength is retested at approximately every 6th session to account for strength gain in maintaining the work load. On days of testing, the strength test replaces one of the four exercise sets. Strength is also tested twice prior to training, at the final training bout, and twice during the post-training follow-up period.
- f. Training sessions consist of three sets of 10 repetitions for each exercise and a 4th set completed at voluntary failure to complete a repetition. Subjects will rest approximately two minutes between each set and approximately 5 minutes between exercises.
- g. Exercise data will be recorded for each subject on the Exercise Data Form.

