- d. **Minimization of Risk:** There are no exclusion criteria specific to this procedure. Risk is low in the study population as compared to younger populations and individuals who may become pregnant.

16. Data Safety and Monitoring Plan

- a. The following plan has been adapted from "Guidelines for Data and Safety Monitoring for Clinical Trials Not Requiring Traditional Data Monitoring Committees" [55].
- b. The study has eligibility criteria that have been precisely defined, as described above, to ensure enrollment of subjects who possess an appropriate risk/benefit ratio. The conservative inclusion and exclusion criteria were developed with input from multiple study physicians. The criteria select of individuals with relatively low risk of adverse events from the study procedures and relatively high probability of benefit from participation. These criteria are assessed and documented in the Medical History and Physical Form prior to active participation. Physician clearance to participate is documented on this form and CPRS.
- c. Safety monitoring will be performed on a frequent and regular basis from enrollment until at least 30 days post-participation for each subject. Monitoring occurs by CPRS query and subject self-report or exam at each research visit as well as during telephone contacts. Thus, during participation monitoring per subject will occur at an average rate of more than once per week.
- d. Monitoring will be proportional to the risk of the phase of the study for the individual. Thus, monitoring may occur four times per week per subject if biopsy and exercise are involved but less than once per week during post-training follow-up when only nutritional supplementation is involved.
- e. Expected adverse events are well-defined as described above and in the informed consent document. All serious adverse events and unexpected adverse events possibly related to participation are also monitored for. The results of monitoring are documented on the submitted monitoring checklist as well as in a CPRS note. This form has both specific expected adverse events and open ended questions for unexpected symptoms as well as space for a detailed note to chart.

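### No liver or kidney test is scheduled on product for about the first 15 weeks; adding the four tests to the existing week-8 draw would give an early value without a new needle stick

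*Combined protocol and SAP*

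**What the plan says.** Section 9 (Supplementation), item j, lists among the safety measures "blood draws for assessment of liver and kidney function at baseline, after completion of the training program and at the end of the study". Section 5.e has samples taken for clinical laboratory analysis "at study entry, after completion of the exercise training program, and upon completion of the study for tests related to eligibility, safety, and research data", and 5.e(4) names the panel: "Clinical labs performed for safety monitoring including AST, ALT, creatinine, and BUN". The two statements agree.

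Product normally starts on the day of the second biopsy and continues for about 42 weeks (Supplementation, item c). Figure 9 ends participation at week 47. Table 6 places draw G at week 8, before the second acute exercise bout and after 2 weeks of product; post-training measures are at week 21. Section 10.d describes "36 exercise sessions that will optimally take 12-weeks though the total time will likely be longer due to rescheduling", so week 21 is the optimal case.

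Between the scheduled tests, section 16.c states: "Monitoring occurs by CPRS query and subject self-report or exam at each research visit as well as during telephone contacts". Section 5.f adds: "The physician may obtain any additional unforeseen medical information that may be needed at enrollment or during participation". Sections 16.f and 16.g let the physician evaluate an event, halt supplementation or withdraw the subject.

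**The concern.** The protocol itself chose liver and kidney tests as part of product safety monitoring. Of the three scheduled tests, the first comes before any product, so it can screen a subject but cannot show a response. The next comes only after training has ended. Until then, an on-product value exists only if a physician orders a test or routine care happens to produce one.

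The subjects are 60 to 80 years old. By name, the entry criteria exclude renal disease only when it requires dialysis (5.c(6)). For the liver they name "Liver cirrhosis or other severe liver disease", and only as a potential exclusion (5.d(15)). Milder disease is left to the entry tests and physician judgment. What is at stake is a modest safety gain: the chance to see an early change while most of the exposure can still be stopped.

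Draw G has a second advantage. It precedes the training program, whereas the week-21 value follows both the product and 36 training sessions. For an individual subject, a change first seen at week 21 cannot be assigned to one or the other.

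**Working it through.** This is schedule arithmetic on the optimal timeline.

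**Inputs.** End of participation: week 47 (Figure 9). Product duration: 42 weeks (Supplementation, item c; Figure 9). Draw G: week 8, and post-training measures: week 21 (Table 6). Servings: two per day, each with 7 g arginine and 7 g glutamine (Table 2).

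**1. Product start.** 47 − 42 = week 5, or week 6 if weeks are counted inclusively (47 − 42 + 1).

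**2. Time on product at the post-training draw.** 21 − 6 = 15 weeks, or 21 − 5 = 16. The Laboratory Aspects section, items I and J, gives 15 weeks of supplementation for the post-training muscle measures, so the plan's own figure is reproduced.

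**3. Time on product at draw G.** 8 − 6 = 2 weeks, or 8 − 5 = 3. Table 6 gives 2 weeks.

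**4. Gain from using draw G.** 15 − 2 = 13 weeks (16 − 3 gives the same).

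**5. As a share of exposure.** Before the first scheduled on-product value: 15/42 = 36% of product weeks. Brought forward: 13/42 = 31%. Product weeks still to come: 42 − 15 = 27 now, against 42 − 2 = 40 with draw G.

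**6. In servings.** At 14 per week, 15 × 14 = 210 servings precede the first scheduled value now, against 2 × 14 = 28 at draw G. The daily amount in the supplement arm is 2 × 7 = 14 g of each amino acid.

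**7. Draws.** A; C and E; G and I; two at K; week 21; week 47: 1 + 2 + 2 + 2 + 1 + 1 = 9, matching the nine stated in section 13.a. A, C and E precede product, and the other six are on product. Liver and kidney tests are scheduled at two of those six, and at none of the four before week 21. Those four are assigned to immune or antibody measures.

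**8. After the change.** Panels per subject go from 3 to 4, and draws stay at 9. Scheduled on-product values before week 21 go from 0 to 1. The remaining intervals are 21 − 8 = 13 weeks and 47 − 21 = 26 weeks. (The 27 weeks in step 5 and the 26 here differ only through inclusive counting.)

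**The case against.** The best reply is that this is a preference and not an error. The schedule is stated twice and consistently, and no section sets an interval that the plan fails to meet. The supplement is sold at retail, its ingredients are described as safe, and item h reports little evidence of risk from controlled studies. Monitoring averages more than once a week, product can be stopped at any time, and the physician can order tests. Nothing in the documents shows that 2 weeks is an informative time for liver or kidney change.

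Most of this stands, and it is why the point is minor. It does not remove the gap: symptom checks and calls yield no laboratory value, and discretionary tests and record queries do not guarantee one.

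Three stronger readings are not supported:

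- **That the product is a known liver or kidney hazard.** Item h does say that "adverse events have occurred in which the relation to underlying disease or the supplement was not discerned", and a reader might take its cautious stance to cover these organs. The conditions it then names are allergies or asthma, herpes and low blood pressure. Its side-effect list includes unspecified blood abnormalities but no liver or kidney injury. Its advice that people with liver disease should not take the product concerns who may enter.
- **That subjects go unmonitored for 15 weeks.** Only scheduled liver and kidney tests are absent.
- **That a particular number of early leavers would have no on-product value.** The plan allows for 20% dropout but says nothing about when subjects leave, so no count can be supported.

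**Conclusion.** The point holds as a minor design improvement. On the optimal schedule, about 15 of 42 product weeks pass before the first scheduled on-product liver or kidney value, and likely more in practice. An existing draw could supply one about 13 weeks earlier. This rests on the nominal weeks in Figure 9 and Table 6 (2 to 3 weeks on product at draw G, 15 to 16 at week 21) and on reading 9.j and 5.e as the full schedule for these tests.

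The benefit is limited. A 2-week value can show only early change, and the later gaps of 13 and 26 weeks are untouched.

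**What to change.** In section 9 (Supplementation), item j, and in section 5.e, add one test time between entry and post-training: *draw G (week 8, before exercise, after about 2 weeks of product)*. Run AST, ALT, creatinine and BUN on it in the hospital clinical lab.

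The protocol sets no action limits for these tests, so state what happens next. The study physician compares the result with entry and records whether to continue, repeat the test, hold product or withdraw the subject, under sections 16.f and 16.g.

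**Cost.** One extra panel per subject who reaches week 8: about 50 for the planned N = 50, and more if more subjects start (Recruitment, item a, requests up to 100 participants). The documents give no panel price. No new visit or needle stick is needed. The panel takes a small share of draw G's blood, within the 60 ml ceiling of section 13.a. The documents do not say how much the T-cell, cytokine and proliferation assays need, so the volume should be checked first. A protocol modification is required.
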